8.7 RESEARCH SAMPLE COLLECTION

Samples for correlative studies may be collected as specified in the study calendar, processed and/or stored for analysis with optional subject consent. All tissue and resulting data will be de-identified and may be shared between MD Anderson and the study supporter (EMD). All samples and data will be tracked utilizing a unique research tracking number that will not be related to any patient identifying information. The sample collections will be reported in the database and a source document will be printed for monitoring purposes. Upon termination of the study, any remaining blood and tissue samples will be transferred and stored in the Melanoma Tissue Bank (MeCore) for future use with an IRB approved protocol.

Biospecimens will be collected according to the study calendar to evaluate the immunological effect of the treatment and SRS. Methods to evaluate this include but may not be limited to:

- FACS on isolated PBMCs
- Serum/plasma collection to assess circulating inflammatory cytokines
- Single stain IHC. Markers include, but are not limited to: CD3, CD4, CD8, CD20 (B cell), CD1a (DC), CD11c (myeloid lineage), Granzyme B (cytotoxic CTLs and NK cells) FOXp3 (Treg cells) and CD3/CD8/CD45RO memory CTL (as proposed in the “Immunoscore” project); IDO and PD-L1 expression.

- Inflammatory expression pattern by Nanostring may be performed on the tumor tissue to mirror evaluations of cytokines and chemokines performed in the peripheral blood

While mechanisms of resistance are relevant and central to all targeted therapy studies, the importance of this evaluation in our proposed study is in delineating the role of mechanisms of resistance assessed in extracranial metastatic melanoma tissues in predicting and describing the patterns of resistance intracranially. It is predicted that the presence or absence of resistance mechanisms extracranially may predict response and progression-free survival intracranially.

Tissue availability permitting, we propose broad investigations on tissue biopsies comparing responders and non-responders, including whole exome sequencing, RNA expression analysis, and reverse phase protein array to examine markers of MAP kinase pathway activity, parallel signaling pathways, RTK activation, and pro and anti-apoptotic factors.

Additionally, we may assess circulating free DNA from serial plasma/serum samples to determine patterns of response and early predictors of resistance. Finally, single cell analyses (including RNA sequencing) may be performed on CSF obtained.

8.7.1 TISSUE

Archival tumor tissue samples obtained outside of this study for other purposes will be collected, if available, from all patients. All samples must be representative formalin-fixed paraffin-embedded (FFPE) tumor specimens in paraffin blocks (preferred) or at least 10 unstained slides, with an associated pathology report, for local testing of tumor PD-L1 expression.

Patients with biopsiable extracranial disease may have tissue collected pretreatment and at Cycle 2 (4 weeks after the start of treatment). Optional Biopsy may be collected at Cycle 5, if accessible, but is not required. If standard of care biopsies are required, additional, optional tissue may be acquired as part of this protocol. Acceptable samples include core-needle biopsies for deep tumor tissue (minimum of three cores) or excisional, incisional, or punch biopsies for cutaneous, subcutaneous, or mucosal lesions.

Acceptable samples include core needle biopsies for deep tumor tissue or lymph nodes or excisional, incisional, punch, or forceps biopsies for cutaneous, subcutaneous, or mucosal lesions. For core-needle biopsy specimens, at least three cores should be submitted for evaluation.

8.7.2 BLOOD

Local laboratory assessments will include the following:

- Hematology (CBC, including RBC count, hemoglobin, hematocrit, WBC count, percent and absolute differential [neutrophils, bands, eosinophils, lymphocytes, monocytes, basophils, and other cells], and platelet count)
- Serum chemistries (glucose, BUN, creatinine, sodium, potassium, magnesium, chloride, bicarbonate, calcium, phosphorus, total and direct bilirubin, ALT, AST, ALP, LDH, total protein, albumin, CPK, and uric acid)
- Coagulation (aPTT and INR)
- Pregnancy test (for women of childbearing potential, including women who have had a tubal ligation)
- Urinalysis (specific gravity, pH, glucose, protein, ketones, and blood)
- Serum samples for auto-antibody testing (PK and ADA samples are all serum)

PK

PRIOR TO INFUSION AND IMMEDIATELY AFTER INFUSION (EOI)

Cycle 1, day 1 and cycle 3 day 1

PRIOR TO INFUSION only:

Cycle 2 and Cycle 6 OR end of treatment (whatever comes first) and followup visit if applicable

ADA:

PRIOR TO INFUSION only

Cycle 1, day 1 (PRETREATMENT); Cycle 3, day 1 and Cycle 6 OR end of treatment (whatever comes first) and followup visit if applicable

- Blood samples for biomarker assays (up to 40 mls will be obtained to fulfill correlative biomarker plans)

Additional Local Testing

Perform the following tests as indicated in Study Flowchart (Table 3) and as clinically indicated.

- Thyroid function testing (TSH, total T3, and free T4)

8.7.3 CEREBROSPINAL FLUID (CSF)

CSF may be collected at the time of routine testing for Leptomeningeal disease (LMD). Leptomeningeal disease occurs when cancer cells migrate from your breast, lung, or some other part of your body to your cerebrospinal fluid (CSF). CSF may be obtained at Cycle 1 Day 1 and Cycle 3 Day 3. Patients will not be asked to undergo an optional lumbar puncture for the purposes of this study. At the time of diagnostic evaluation, additional CSF may be obtained for the purposes of this study.

8.8 TUMOR IMAGING AND ASSESSMENT OF DISEASE

All subjects will undergo CT scanning and MRI of the brain at the time points specified in the Schedule of Events. CT and MRI scans will be assessed locally per the modified RECIST 1.1, RANO-BM, and iRANO criteria. Up to 5 systemic and 5 brain lesions will be followed for efficacy per the criteria. Patients with biopsiable extracranial disease may have tissue collected.

8.9 THERAPY ADMINISTRATION

Drug	Dose	Dose Frequency	Route of Administration	Treatment Period	Use
Pimasertib	30-60 mg	BID	Oral	Continuously on 28-day cycles	Experimental
Bintrafusp Alfa (M7824)	1200 mg	Every 2 Weeks	IV Infusion	Once every 2 Weeks on 28 day cycles	Experimental

8.10 MANAGEMENT OF PATIENTS WITH DISEASE PROGRESSION

In the absence of unacceptable toxicity, patients who meet criteria for disease progression will be permitted to continue study treatment if they meet all of the following criteria:

- Evidence of clinical benefit, as determined by the principal investigator following a review of all available data
- Absence of symptoms and signs (including laboratory values) indicating unequivocal progression of disease
- Absence of decline in ECOG Performance Status that can be attributed to disease progression
- Absence of tumor progression at critical anatomical sites (e.g., leptomeningeal disease) that cannot be managed by protocol-allowed medical interventions

8.11 SUPPORTIVE CARE GUIDELINES

Subjects should receive appropriate supportive care measures as deemed necessary by the treating principal investigator. Suggested supportive care measures for the management of adverse events with potential immunologic etiology are outlined below. Where appropriate, these guidelines include the use of oral or intravenous treatment with corticosteroids as well as additional anti-inflammatory agents if symptoms do not improve with administration of corticosteroids. Note that several courses of steroid tapering may be necessary as symptoms may worsen when the steroid dose is decreased. For each disorder, attempts should be made to rule out other causes such as metastatic disease or bacterial or viral infection, which might require additional supportive care. The treatment guidelines are intended to be applied when the principal investigator determines the events to be related to pimasertib and bintrafusp alfa (M7824).

Note: if after the evaluation the event is determined not to be related, the principal investigator does not need to follow the treatment guidance (as outlined below). Refer to Section for dose modification.

It may be necessary to perform conditional procedures such as bronchoscopy, endoscopy, or skin photography as part of evaluation of the event.

- **Pneumonitis:**
 - For **Grade 2 events**, treat with systemic corticosteroids. When symptoms improve to Grade 1 or less, steroid taper should be started and continued over no less than 4 weeks.
 - For **Grade 3-4 events**, immediately treat with intravenous steroids. Administer additional anti-inflammatory measures, as needed.
 - Add prophylactic antibiotics for opportunistic infections in the case of prolonged steroid administration.
- **Diarrhea/Colitis:**

Subjects should be carefully monitored for signs and symptoms of enterocolitis (such as diarrhea, abdominal pain, blood or mucus in stool, with or without fever) and of bowel perforation (such as peritoneal signs and ileus).

- All subjects who experience diarrhea/colitis should be advised to drink liberal quantities of clear fluids. If sufficient oral fluid intake is not feasible, fluid and electrolytes should be substituted via IV infusion. For Grade 2 or higher diarrhea, consider GI consultation and endoscopy to confirm or rule out colitis.
 - For **Grade 2 diarrhea/colitis**, administer oral corticosteroids.
 - For **Grade 3 or 4 diarrhea/colitis**, treat with intravenous steroids followed by high dose oral steroids.
 - When symptoms improve to Grade 1 or less, steroid taper should be started and continued over no less than 4 weeks.
- **Type 1 diabetes mellitus** (if new onset, including diabetic ketoacidosis [DKA]) or \geq Grade 3 Hyperglycemia, if associated with ketosis (ketonuria) or metabolic acidosis (DKA)
 - For **T1DM or Grade 3-4 Hyperglycemia**
 - Insulin replacement therapy is recommended for Type I diabetes mellitus and for Grade 3-4 hyperglycemia associated with metabolic acidosis or ketonuria.
 - Evaluate patients with serum glucose and a metabolic panel, urine ketones, glycosylated hemoglobin, and C-peptide.
- **Hypophysitis:**
 - For **Grade 2** events, treat with corticosteroids. When symptoms improve to Grade 1 or less, steroid taper should be started and continued over no less than 4 weeks. Replacement of appropriate hormones may be required as the steroid dose is tapered.
 - For **Grade 3-4** events, treat with an initial dose of IV corticosteroids followed by oral corticosteroids. When symptoms improve to Grade 1 or less, steroid taper should be started and continued over no less than 4 weeks. Replacement of appropriate hormones may be required as the steroid dose is tapered.
- **Hyperthyroidism or Hypothyroidism:**

Thyroid disorders can occur at any time during treatment. Monitor patients for changes in thyroid function (at the start of treatment, periodically during treatment, and as indicated based on clinical evaluation) and for clinical signs and symptoms of thyroid disorders.

- **Grade 2** hyperthyroidism events (and **Grade 2-4** hypothyroidism):
 - In hyperthyroidism, non-selective beta-blockers (e.g. propranolol) are suggested as initial therapy.
 - In hypothyroidism, thyroid hormone replacement therapy, with levothyroxine or liothyroinine, is indicated per standard of care.
- **Grade 3-4** hyperthyroidism

- Treat with an initial dose of IV corticosteroid followed by oral corticosteroids. When symptoms improve to Grade 1 or less, steroid taper should be started and continued over no less than 4 weeks. Replacement of appropriate hormones may be required as the steroid dose is tapered.
- **Hepatic:**
 - For **Grade 2** events, monitor liver function tests more frequently until returned to baseline values (consider weekly).
 - Treat with IV or oral corticosteroids
 - For **Grade 3-4** events, treat with intravenous corticosteroids for 24 to 48 hours.
 - When symptoms improve to Grade 1 or less, a steroid taper should be started and continued over no less than 4 weeks.
- **Renal Failure or Nephritis:**
 - For **Grade 2** events, treat with corticosteroids.
 - For **Grade 3-4** events, treat with systemic corticosteroids.
 - When symptoms improve to Grade 1 or less, steroid taper should be started and continued over no less than 4 weeks.
- **Ocular reactions:**
 - Visual disturbances: for Grade 2 events, pimasertib should be discontinued until full resolution of the event and recovery of vision, assuming resolution of the event within 2 weeks to Grade 1 or less.
 - In case of visual symptoms but without vision loss, the treatment will not be discontinued.
- **Skin reactions:**
 - Early introduction of oral tetracyclines and medium to high potency topical treatment (such as 1% hydrocortisone cream with moisteriser) should be initiated in case of Grade 1 or 2 skin reaction. The dose of the investigational treatment should not be decreased.
 - If a subject experiences a severe skin reaction (Grade ≥ 3), pimasertib therapy must be interrupted and may be resumed at the original dose when the reaction has resolved to Grade 1 or 2. In case of second or third occurrence of severe skin reaction pimasertib therapy must again be interrupted. Treatment may only resume at a lower dose level (45 mg BID after the second occurrence and 30 mg BID after the third occurrence) if the reaction has resolved to Grade 1 or 2. In case of further recurrence another dose reduction may be proposed.

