	
 • In case of alternative explanations, hold study treatment until the event recovers to Grade ≤ 1
Grade 4	
 • Treatment must be permanently discontinued if no alternative explanation is identified.
Tumor Bleeding	
Grade ≥ 2	
 • Study treatment must be held till the event recovers to Grade ≤ 1 • Permanently discontinue treatment if the Investigator considers the participant to be at risk for additional severe bleeding.

Ocular toxicity

If a subject experiences Retinal Vein Occlusion the pimasertib treatment must be immediately stopped. Appropriate follow-up and treatment measures must be taken by the treating ophthalmologists.

If a subject shows a symptomatic serous retinal detachment: Withhold treatment for ≤ 3 weeks, if improved to grade 0/1, resume at same dose level. If not improved, resume at the lower dose level or permanently discontinue pimasertib treatment. Management should be discussed with Principal Investigator and ophthalmologist.

Elevation of Serum Creatine Phosphokinase

Subjects should be advised to immediately report any muscle pain, tenderness or weakness, or any macroscopic myoglobinuria (tea-colored urine). Subject-reported muscle symptoms or urine discoloration should be investigated with CPK measurements and urinalysis for myoglobinuria.

CPK measurement should be at screening and every 4 weeks; at any time for symptomatic patients. Assess with differentiation if irAE or due to Pimasertib; including DD presence/absence of further symptomatic findings: full history (including commeds), exercises, training, muscular injury, muscular injections, CPK isoenzymes, and etc.

CPK increase G4: Withhold pimasertib treatment for ≤ 3 week

Any CPK elevation and myalgia: If improved to grade ≤ 3 , resume at lower dose level, if not improved within 3 weeks, permanently discontinue pimasertib treatment.

Dehydration

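### The Section 8.11 rule to continue treatment for visual symptoms without vision loss makes no exception for two retinal diagnoses that Section 6.2.3 says must be stopped or held

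*Combined protocol and SAP*

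**What the plan says.** Section 8.11 (Supportive Care Guidelines) has two bullets on ocular reactions. The first concerns visual disturbances: "for Grade 2 events, pimasertib should be discontinued until full resolution of the event and recovery of vision", on the assumption that the event settles to Grade 1 or less within 2 weeks. The second reads: "In case of visual symptoms but without vision loss, the treatment will not be discontinued". Neither names retinal vein occlusion or serous retinal detachment.

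Section 6.2.3 (Dose Modification, ocular toxicity) has a rule for each of those diagnoses.

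- Retinal vein occlusion: "If a subject experiences Retinal Vein Occlusion the pimasertib treatment must be immediately stopped". No grade and no restart rule are given.
- Serous retinal detachment: "If a subject shows a symptomatic serous retinal detachment: Withhold treatment for" up to 3 weeks. After that, "if improved to grade 0/1, resume at same dose level". Otherwise, "If not improved, resume at the lower dose level or permanently discontinue pimasertib treatment".

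The introduction to 8.11 sets the status of its guidance: "Suggested supportive care measures for the management of adverse events with potential immunologic etiology are outlined below". It applies when the principal investigator judges the event related to the study drugs.

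**The concern.** Section 8.11 starts from a symptom and says carry on. Section 6.2.3 starts from a diagnosis and says stop or hold. A patient who has one of the two diagnoses, with visual symptoms but preserved vision, falls under both. An investigator who follows 8.11 to the letter would keep that patient on pimasertib through an event for which 6.2.3 orders a stop or a hold.

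The protocol foresees these risks. Exclusion criterion 18 bars patients with a history of retinal vein occlusion or an eye condition that predisposes to it. Section 8.3 uses the baseline eye examination to look for retinal pathology that raises the risk of occlusion or central serous retinopathy. What is at stake is patient safety in a small number of cases, not the estimation of any endpoint.

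**Working it through.** No arithmetic applies. The check sets the rules side by side and asks when they collide.

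| Rule | Trigger | Depends on vision loss? | Instruction |
|---|---|---|---|
| 8.11, second ocular bullet | Visual symptoms, any cause, any grade | Yes: applies when vision is not lost | Do not discontinue the treatment |
| 6.2.3, vein occlusion | The diagnosis | No | Stop pimasertib immediately |
| 6.2.3, serous detachment | The diagnosis, with symptoms | No | Withhold treatment for up to 3 weeks |

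1. **Can the triggers overlap?** Nothing in the text prevents it. For serous detachment, 6.2.3 itself presupposes symptoms and does not require loss of vision. For vein occlusion the documents do not describe the presentation, so it is an assumption that it can occur with symptoms and preserved vision.

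2. **What does *discontinued* mean in 8.11?** The preceding bullet uses the word for a stop that lasts until the event resolves ("for Grade 2 events, pimasertib should be discontinued until full resolution of the event and recovery of vision"). A temporary hold is therefore a natural meaning. It is not the only one, because the skin bullets in the same section speak of therapy being interrupted.

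3. **What does *the treatment* mean in 8.11?** The first ocular bullet names pimasertib; the second does not. It may mean pimasertib or the whole two-drug regimen.

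4. **Vein occlusion.** If *the treatment* includes pimasertib, 6.2.3 says stop and 8.11 says do not: a conflict. If it means only the regimen as a whole, pimasertib can be stopped while bintrafusp alfa continues, and both rules are met.

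5. **Serous detachment.** If *discontinued* covers a hold, 6.2.3 says withhold and 8.11 says do not: a conflict. If it means only a permanent stop, the sections collide only when the event has not improved and the permanent option in 6.2.3 is chosen. A Grade 1 detachment already meets the 6.2.3 restart threshold, so the practical difference there may be small. At Grade 2 the first 8.11 bullet also stops pimasertib.

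6. **Does any text settle the order?** Sections 6.2.3, 8.3 and 8.11 were read for an exception or a statement of precedence. None gives one. Section 8.3 covers only the timing and content of eye examinations. Section 8.11 refers the reader to dose modification in general terms, which is not an exception.

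**The case against.** The best reply is that 6.2.3 already handles both diagnoses. It is specific, it uses mandatory language for vein occlusion, and it brings ophthalmologists into the management of both. Section 8.11 describes its measures as suggested and frames them around immunologic causes. A careful investigator would follow 6.2.3. That stands, and it is why the point is small. It does not remove the inconsistency, because the 8.11 sentence is phrased as a directive and no text subordinates it.

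Three stronger readings are tempting, and the documents support none of them.

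- A reader might infer that the vein occlusion conflict is inescapable on any reading. It is not: if *the treatment* means the whole regimen, stopping pimasertib alone breaches neither rule.
- A reader might treat the wording "Refer to Section for dose modification", which lacks a section number, as a broken cross-reference and further evidence. The number may have been lost when the text was extracted, so it should not be counted. The point does not need it.
- A reader might conclude that the protocol must require an eye examination for every new visual symptom before dosing continues, since scheduled examinations are only at baseline, every 12 weeks and end of treatment. The inconsistency does not establish that need. Section 8.11 already allows conditional procedures in the evaluation of an event, and a mandatory examination would be a new procedure beyond the wording fault.

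**Conclusion.** The 8.11 sentence is wrong as written, in a narrow way. It states without exception a continue rule that, on its literal reading, contradicts the stop rule for retinal vein occlusion and the hold rule for symptomatic serous retinal detachment in 6.2.3.

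The conclusion rests on two readings and one assumption. *The treatment* must include pimasertib. *Discontinued* must cover a temporary hold, as it does in the preceding bullet; this matters mainly for serous detachment. And these events must sometimes present with visual symptoms while vision is preserved.

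The size cannot be put as a number of patients, because the documents give no rate for either event. In practice 6.2.3 would probably prevail. No endpoint, sample size, stopping boundary or analysis changes.

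**What to change.** Keep the 8.11 sentence ("In case of visual symptoms but without vision loss, the treatment will not be discontinued") and add one clause at its end: *except for retinal vein occlusion or symptomatic serous retinal detachment, which are managed per Section 6.2.3.*

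This makes 6.2.3 govern both diagnoses under every reading discussed above. It requires no additional eye examination and no change to the schedule of assessments, the data collected or the analysis. The cost is one clause in a protocol amendment. If it changes practice at all, it may lead to an occasional pimasertib stop or short hold that 6.2.3 already calls for.

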3.0 STUDY DESIGN

This study is an open-label Phase I/II trial to determine the safety and efficacy of pimasertib in combination with Bintrafusp Alfa (M7824) in patients with brain metastases. The Phase I study will accrue patients with melanoma, lung, and breast cancers to a dose escalation phase as described below. The Phase II study will include expansion cohorts, of 10 patients each with melanoma, lung, and breast brain metastases, to better characterize the safety profile and efficacy of the combination and its impact on time to intracranial progression.

We have also incorporated an early imaging time point to allow the application of SRS to intracranial lesions that are either progressing or not responding. This decision will be made in the context of multi-disciplinary care provided at the MD Anderson Brain Metastasis Clinic.

[figure not shown]
Phase I:

The phase I dose finding part of the study is to determine the recommended phase II dose (RP2D) of Bintrafusp Alfa (M7824) + pimasertib in patients with intracranial metastasis. The planned DL1 and DL2 doses are Bintrafusp Alfa (M7824) flat dose of 1200 mg every 2 weeks and pimasertib 45 mg PO BID (Dose Limit or DL1) and 60 mg PO BID (DL2), and fallback doses DL-1 are Bintrafusp Alfa (M7824) flat dose of 1200 mg every 2 weeks and Pimasertib at 30 mg PO BID. Every cycle will be 28 days. We will enroll up to 12 patients to the Phase I portion (18, should the trial de-escalate to DL-1). The standard “3+3” design will be employed to determine the RP2D. If DL1 is considered too toxic, DL-1 will be explored; if unacceptable toxicity is observed at DL-1, alternative dose schedules may be evaluated in an amendment. The recommended phase II dose (RP2D) is defined as the highest dose level with no more than 1 patient with DLT out of 6 patients that are treated. Please note that the study plans on enrolling up to 2 cohorts in Phase 1 of the trial (the 45mg and either the 30 or 60 mg, depending on the safety of Cohort 1).

Phase II:

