6.2.1 DOSAGE AND ADMINISTRATION

Pimasertib will be administered orally at a dose of either 30 mg, 45 mg, or 60 mg twice daily (BID) continuously, based on RP2D. Starting dose level for phase 1 is 45mg orally BID.

Pimasertib can be taken in fasted state or after a light meal. The subject will be instructed to swallow the capsules without biting into breaking or opening them, or attempting to dissolve the content in water prior to taking them.

A time window of 12 ± 3 hours between the administration of the morning and evening dose of pimasertib is considered acceptable.

Table 1: Trial Treatments and Description

Product	Dose	Dose Frequency	Route of Administration	Appearance	Storage Conditions (per label)
BINTRAFUSP ALFA (M7824)	1200 mg	Every 2 Weeks	IV Infusion		2°C – 8°C
Pimasertib	60mg ^A	Twice Daily	Oral		

A=DEPENDING ON THE PHASE OF THE STUDY THE PARTICIPANT IS PARTICIPATING IN, THEY COULD RECEIVE 30-60MG OF THE DRUG.

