6.2.5 RESUMPTION OF TREATMENT AFTER DOSE DELAY

Patients may resume therapy at the same doses after dose interruption as long as they continue to meet the treatment safety parameters.

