Pregnancy Test – Urine or Serum -HCG ^d	X			X		X	X	X	X	X	X	X			
Coagulation ^e	X														
CBC with Differential ^k	X	X	X	X	X	X	X	X	X	X	X	X		X	
CMP ^m	X	X	X	X	X	X	X	X	X	X	X	X		X	
Urinalysis	X			X		X	X	X	X	X	X	X			

Trial Period:	Screening Phase	Treatment Cycles ^a								End of Treatment	Post-Treatment				
		To be repeated beyond 8 cycles				Discontinuation					Safety Follow-up	Follow Up Visits ^b	Survival Follow-Up ^p		
Treatment Cycle/Title:	Screening	C1 D1	C1 D15	C2 D1	C2 D15	3	4	5	6	7	8				
Scheduling Window (Days):	-28 to -1			± 3		± 3	± 3	± 3	± 3	± 3	± 3	At time of Discontinuation	30 days post discontinuation ± 7	Every 6 weeks post discontinuation ± 7	Every 12 weeks ± 7
Lactate dehydrogenase (LDH)	X			X		X	X	X	X	X	X	X			
T3, FT4 and TSH	X	X				X		X		X		X			
Creatinine Phosphokinase	X	X		X		X	X	X	X	X	X	X			
HIV, HBV, HCV Testing	X														
Efficacy Measurement															
Tumor Imaging & Assessment of disease: MRI ^f	X			X		X	X	X	X	X	X	X			
Tumor Imaging & Assessment of disease: CT's ^f	X					X		X		X					
Tumor Biopsies/Archival Tissue Collection/Correlative Studies Blood															

Trial Period:	Screening Phase	Treatment Cycles ^a								End of Treatment	Post-Treatment				
		To be repeated beyond 8 cycles				Discontinuation					Safety Follow-up	Follow Up Visits ^b	Survival Follow-Up ^p		
Treatment Cycle/Title:	Screening	C1 D1	C1 D15	C2 D1	C2 D15	3	4	5	6	7	8				
Scheduling Window (Days):	-28 to -1			± 3		± 3	± 3	± 3	± 3	± 3	± 3	At time of Discontinuation	30 days post discontinuation ± 7	Every 6 weeks post discontinuation ± 7	Every 12 weeks ± 7
Archival Tissue ^g	X														
Serial Biopsy ^h	X			X			X								
Blood/Tissue Collection	X			X		X	X	X	X	X	X				
Correlative Studies ^j	X			X			X				X				
PK and ADA		X		X		X		X			X		X		
CSF ⁱ (optional)	X	X				X									

- a Cycles are 4 weeks (28 days) in duration
- b Patients who discontinue trial treatment for reasons other than disease progression will move into the Follow-Up phase. Patients will be seen every 6 weeks for the first year, then every 12 weeks thereafter up to 2 years.
- c M7824 1200 mg every 2 weeks. Pimasertib will be administered at 60mg twice daily. (30 to 60 mg depending on phase)
- d See Page 78 if a woman of child-bearing potential becomes pregnant while on study. Negative pregnancy test within 3 days prior to initiation of dosing and continuation of birth control for 120 days after last dose of drug.

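### The re-dosing ladder for severe skin reactions (45 then 30 mg BID) is a reduction at both steps only for patients assigned pimasertib 60 mg BID

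*Combined protocol and SAP*

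**What the plan says.** Section 8.11 (Supportive Care Guidelines, skin reactions) requires pimasertib to be interrupted for a Grade 3 or worse skin reaction. After the first such reaction it may restart at the original dose once the reaction has settled to Grade 1 or 2. For the second and third: "Treatment may only resume at a lower dose level (45 mg BID after the second occurrence and 30 mg BID after the third occurrence", again subject to recovery to Grade 1 or 2. The item closes with "In case of further recurrence another dose reduction may be proposed".

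The dose a patient starts from is not fixed. Section 6.2.1 states: "Pimasertib will be administered orally at a dose of either 30 mg, 45 mg, or 60 mg twice daily (BID) continuously, based on RP2D". Sections 3.0 and 9.1 name the levels: DL-1 is 30 mg BID, DL1 is 45 mg BID and DL2 is 60 mg BID. The first cohort is treated at DL1, and section 3.0 describes the phase I cohorts as "the 45mg and either the 30 or 60 mg, depending on the safety of Cohort 1".

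Three other places bear on restarting or on the assigned dose:

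- Section 6.2.3, for symptomatic serous retinal detachment: "If not improved, resume at the lower dose level or permanently discontinue pimasertib treatment". The CPK rule in the same section also refers to a lower level without naming a dose.
- Section 6.2.5, the general rule: "Patients may resume therapy at the same doses after dose interruption".
- Section 8.0, Table 3, footnote c: "Pimasertib will be administered at 60mg twice daily. (30 to 60 mg depending on phase".

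**The concern.** The skin rule combines a relative instruction (the restart dose must be lower) with two absolute doses. The two agree only if the patient began at 60 mg BID. For the other assignable doses, the words and the numbers point in different directions at one or both steps.

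The affected doses are not remote cases. Phase I opens at 45 mg BID, and 30 mg BID is the planned fallback. Either could become the recommended phase II dose, at which 30 patients in total are planned (sections 3.0 and 9.2). If so, the ladder would be wrong for everyone at that dose who needs it.

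What is at stake is consistent and safe re-dosing after repeated severe drug-related toxicity. For a patient on 45 mg BID with a second severe reaction, one physician could restart at 45 mg because that figure is printed, and another at 30 mg because the text demands a reduction.

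**Working it through.** **Inputs.** Assigned doses A = 60, 45 or 30 mg BID (sections 3.0, 6.2.1 and 9.1). Printed restart doses P = 45 mg BID at the second occurrence and 30 mg BID at the third (section 8.11). The first restart is at the original dose, so A is also the dose in use when the second reaction occurs.

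**Formula.** Change against assigned dose = P/A - 1. The rule requires a negative value.

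| Assigned dose | Second occurrence (P = 45) | Third occurrence (P = 30) |
|---|---|---|
| 60 mg BID | 45/60 - 1 = -25% | 30/60 - 1 = -50% |
| 45 mg BID | 45/45 - 1 = 0% | 30/45 - 1 = -33% |
| 30 mg BID | 45/30 - 1 = +50% | 30/30 - 1 = 0% |

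The printed dose is lower than assigned in 3 of 6 cells, equal in 2 and higher in 1. In the +50% cell, the printed figure is 2 × 45 = 90 mg/day against an assigned 2 × 30 = 60 mg/day.

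**Check against the current dose.** From 60 mg BID the sequence is 60, 45, 30, and both steps are reductions. From 45 mg BID, taking the printed figure at the second occurrence gives 45, 45, 30, so the first step fails. Following the words instead, and dropping to 30 mg at the second occurrence, gives 45, 30, 30, so the third-occurrence step fails. Neither reading gives two reductions from 45 mg BID.

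**Defined levels below the assigned dose.** From 60 mg there are two (45 and 30), from 45 mg one (30), and from 30 mg none. At 30 mg BID the relative instruction therefore cannot be met with any defined level, even at the second occurrence.

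**Does another section settle it?** Section 6.2.5 permits the same dose, which is what the skin rule excludes at these occurrences. The relative wording in section 6.2.3 covers ocular and CPK events, and no dose-level table accompanies it. Table 1 and Table 3 footnote c both qualify their 60 mg entry with a 30 to 60 mg range, but section 8.11 carries no such qualifier. No sentence confines the skin ladder to DL2 or presents its doses as examples.

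**The case against.** The strongest reply is that the requirement for a lower dose governs and the bracketed doses only illustrate it. The protocol uses 60 mg as its template figure elsewhere (Table 1, Table 3 footnote c, the pill diary example in Appendix 10), and 45 then 30 is the ladder from 60. On that reading nobody would raise a dose after a second severe reaction, and a 45 mg patient would drop to 30 mg. This has force: the text is not an order to escalate, and the +50% cell arises only if the governing words are ignored and only if DL-1 is opened. At 45 mg BID, second occurrence, the words do point to an answer. But nothing marks the doses as illustrative, and from 30 mg BID the words lead to no defined level.

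Second, section 8.11 offers suggested care in a single-centre trial, "intended to be applied when the principal investigator determines the events to be related to pimasertib" and bintrafusp alfa, and section 6.2.3 provides for principal investigator and dermatology input on drug-related skin lesions. That lowers the practical risk. It does not remove it, because the skin item itself uses mandatory language on interruption and restart.

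Third, leaving later reductions open may be deliberate, and the 15 mg capsules (section 6.2) make a dose below 30 mg physically possible. That is a fair defence of the clause on further recurrence. It does not help where the gap appears earlier: at the third occurrence from 45 mg BID, or the second from 30 mg BID.

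**Conclusion.** The inconsistency is real and should be corrected. The printed ladder works as written for one of the three assignable doses. Measured against the assigned dose, it is not a reduction in 3 of 6 combinations. The conflict is most practical at 45 mg BID, second occurrence, because 45 mg is the phase I starting dose.

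The six combinations are not equally likely, so 3 of 6 describes the rule and does not measure risk. Only patients with at least two Grade 3 or worse skin reactions judged drug-related are affected. The documents give no rate for these, so no count is offered. The conclusion assumes only that DL-1, DL1 and DL2 are the complete set of defined levels. It has no bearing on the primary endpoints, sample size, escalation rule or toxicity stopping boundaries.

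**What to change.** In the skin-reactions item of section 8.11, replace the two fixed doses with a relative rule: one defined level below the assigned dose at the second occurrence and one further level down at the third, using the sequence 60, 45, 30 mg BID.

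Add what happens when no lower level is defined. This arises at the second occurrence from 30 mg BID, at the third from 45 mg BID, and at any further recurrence from 60 mg BID. The choice between permanent discontinuation of pimasertib and a newly defined lower level belongs to the sponsor's clinical team.

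The cost is a wording amendment to one rule, with no effect on sample size, error rates or analysis.
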